6.1 Glucose Spikes

Excessive refined carbohydrate intake can lead to an excess of glucose in the blood. The pancreas works to stabilize blood sugar levels by secreting a surge of insulin to help move glucose into our cells or storage. However, even after excess glucose has been cleared, our insulin levels remain high. This leads to an overcorrection and subsequent low blood sugar. Unstable blood sugar is linked to depressed and anxious mood, “brain fog,” impaired cognitive performance, disturbed sleep, chronic pain, and poor workout performance. Conversely, stable blood sugar can boost our energy levels, mood, productivity, and overall well-being.²

Glucose variability is not only a problem for individuals with diagnosed health conditions relating to glucose. According to a 2018 study, “16 out of 20 participants who were classified as normal on standard clinical tests experienced severe post-meal glucose spikes that reached into the prediabetic range 15 percent of the time”³. Additionally, a 2009 study of glucose spikes studied more than 15,000 healthy, non-diabetic individuals. It found that elevated 2-hour postprandial glucose increased the risk of cardiovascular and all-cause death significantly⁴.

Excessive post-meal blood glucose spikes are an independent risk factor for a host of chronic conditions, including diabetes, cardiovascular disease, stroke, kidney failure, cancer, retina damage, and cognitive decline. Eating to promote stable blood sugar and developing metabolic flexibility is critical to supporting your long-term health and wellbeing⁵.

6.2 Canagliflozin

Canagliflozin is an SGLT2 inhibitor. It is a compound also known under the name Invokana. Canagliflozin is used (with diet and other medications) to treat type 2 diabetes (a condition in which the body does not use insulin normally and therefore cannot control the amount of sugar in the blood). Canagliflozin works by blocking SGLT2, a protein that helps the body reabsorb glucose from urine to the bloodstream. The body instead excretes glucose through urine.¹

Clinical studies

Canagliflozin Tablets were studied as monotherapy and as combination therapy to metformin, insulin, or other treatments. The treatment effects on HbA1c levels and one-hour postprandial glucose levels are summarized for four placebo-controlled, double-blind, randomized studies conducted in the United States. The placebo-subtracted treatment differences, which are summarized below, were statistically significant for both variables in all of these studies.

Study 1: (n=584) This study showed that canagliflozin caused a significant reduction in blood sugar soon after taking canagliflozin. This was true at both doses of 100 mg canagliflozin as well as with 300 mg of canagliflozin. HbA1c levels dropped by 0.8 mg/dl with the 100 mg treatment and by 1.0 mg/dl with the 300 mg treatment.¹

Study 2: (n=20) Canagliflozin reduced postprandial plasma glucose by 35% and insulin excursions by 43% in this study (P < 0.001 for both). It also increased urinary glucose excretion (UGE_{0-6h}, 18.2 ± 5.6 vs. <0.2 g; P < 0.001). It reduced blood glucose by increasing glucose excretion.⁶

Study 3: (n=1450) Canagliflozin at 100 mg and 300 mg reduced A1c levels by -0.65% and -0.74%, respectively, over a treatment period of 104 weeks. Also, it reduced systolic blood pressure by -2.0 mmHg with the 100 mg dose and by -3.1 mmHg with the 300 mg dose.⁷

Study 4: (n=4401) Canagliflozin was generally well tolerated⁸. Adverse events related to the kidneys were lower with canagliflozin treatment of 100 mg, with an incidence of 60.2 per 1,000 vs an rate of 84.0 per 1,000 of the control group.⁹

6.3 Current standard of care and alternative treatments for glucose spikes

Current standard of care for glucose control in diabetics revolves around the use of diet, and exercise, in combination with different medicines and molecules, such as Metformin, Insulin, Sulfonylureas, SGLT-2 inhibitors, and acarbose. In healthy, non-diabetic individuals, the main way to mitigate blood sugar spikes is to rely on diet and exercise. Non-diabetic individuals have to find ways to substitute sugars or carbohydrates from their diet to prevent spikes. Similarly, they exercise in order to have normally-functioning glucose disposal, or stay well hydrated by drinking water after consuming starchy meals.¹⁰ Glucose spikes often go untreated, and are common in healthy, non-diabetic individuals after high carbohydrate intake.

6.4 Rationale and Hypothesis

Canagliflozin is a prime candidate to reduce glucose spikes and blood sugar. It has consistently acted to treat type 2 diabetes and has been shown to improve biomarkers such as fasted glucose and glucose spikes.

The current FDA-approved use of the drug is for use together with diet and exercise to treat type 2 diabetes. Canagliflozin is sometimes used in combination with insulin or other diabetes medications taken orally. It is routinely prescribed at equal or higher doses than the ones proposed in this trial.

AgelessRx Trial doses: 100 mg and 150 mg doses, taken every day and every-other day, respectively.

FDA-approved dose: Maximum recommended dose: 300 mg once daily.

Some possible side effects at the FDA-approved doses include hypoglycemia, indigestion, nausea, UTI, increased urination or thirst, hypotension, ketoacidosis, dehydration, and headache. The doses we propose have potential for some side effects, though the drug is generally well tolerated.

This trial will use a lower dose than the maximum one recommended by the FDA. We are using a maximum of 150 mg in one day vs the maximum of 300 mg each day recommended by the FDA. At this smaller dose, side effects are less common⁸. This dose has been shown to be generally safe.

Our hypothesis is three-fold:

1. Canagliflozin can be used safely and is well tolerated at doses of 100 mg per day or 150 mg every two days in healthy, non-diabetic individuals.
2. Usage of canagliflozin at these doses can effectively reduce glucose spikes (and their detrimental effects) and blood sugar levels measured by CGM in a healthy population.
3. Usage on alternate days will be effective as measured by our endpoints.

7. Objectives

7.1 Primary Objective

To measure the effects that Canagliflozin intervention has on blood glucose at the tested doses. This will be measured by observing glucose spikes following a high-carbohydrate meal at the tested doses, as well as by studying baseline glucose levels with and without canagliflozin.

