Objectives: Primary: To measure the effects that canagliflozin intervention has on reducing average glucose in healthy individuals. Secondary: To assess the tolerability and side effects and urinary glucose excretion following the pulsatile dosing protocol.
Methodology: 
1. Candidates will be offered participation through word of mouth and AgelessRx platform.2. Once screened and enrolled, participants will be randomized into one of two arms (A and B) and provided with all items included in the materials list below.3. Arms A & B:
a Day 0: Participants will attach a continuous glucose monitor (CGM) and follow instructions for calibration period.b Day 1 – 14: Participants will take morning blood pressure readings, and keep dietary intake journal via Lifesum.c Day 7: Participant completes Urine Collection Kit #14. Arm A:
a Day 8 - 14: Participants take 100mg Invokana (canagliflozin) with first meal daily.b Day 15: 24h after final dose, Participant completes Urine Collection Kit #2c Day 16: 48h after final dose, Participant completes Urine Collection Kit #3d Day 17: 72h after final dose, Participant completes Urine Collection Kit #45. Arm B:
a Day 8 - 14: Participants take 150mg Invokana (canagliflozin) with first meal daily, every other day for a total of 4 doses.b Day 15: 24h after final dose, Participant completes Urine Collection Kit #2c Day 16: 48h after final dose, Participant completes Urine Collection Kit #3d Day 17: 72h after final dose, Participant completes Urine Collection Kit #4
Number of subjects planned: Up to 20 healthy individuals via telehealth administration, 10 individuals in each Arm.

Diagnosis and main criteria for inclusion: Subjects will be healthy and of any sex, any ethnicity, and any age from 18-85. Participants must be approved by AgelessRx Medical Team for use of canagliflozin. They also require a CGM-compatible mobile device ([defined here](#))

Test product, dose, and mode of administration (proposed): The tablets will be from the brand Invokana and have a dosage of 100 mg or 300 mg per tablet. Investigational drugs are to be administered orally. Investigational drugs will be provided by Curexa Pharmacy, [name]

Duration of treatment: 7 days

Criteria for evaluation:

Efficacy:

- CGM data
- Urinary glucose

Safety:

- Tolerability

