10.3 Safety and efficacy evaluations

The primary endpoint, average glucose, will be assessed by examining blood glucose (mg/dL) area under curve as measured by CGM. Glucose data on days without canagliflozin treatment will serve as a control.

The secondary endpoints of safety and tolerability and urinary glucose excretion will also be assessed. Safety and tolerability will be measured by adverse event reporting, blood pressure monitoring, and by comparing treatment tolerability survey results with control tolerability results through subjective surveys. Urinary glucose excretion will be measured by at-home glucose testing strips.

11 Investigational Product

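### Section 7.1 relies on glucose spikes after a high-carbohydrate meal, but the available text schedules no such meal and defines no spike endpoint or analysis

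*Combined protocol and SAP*

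**What the plan says.** Section 7.1 gives the primary objective two measures. The first concerns spikes: "This will be measured by observing glucose spikes following a high-carbohydrate meal at the tested doses". The second concerns glucose on and off the drug: "as well as by studying baseline glucose levels with and without canagliflozin". Spikes are also a stated purpose in the Study Design entry on the title page, and hypothesis 2 in Section 6.4 begins "Usage of canagliflozin at these doses can effectively reduce glucose spikes".

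The rest of the plan reads differently:

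- **Synopsis, primary objective:** "To measure the effects that canagliflozin intervention has on reducing average glucose in healthy individuals". Spikes are not mentioned.
- **Schedule (Synopsis and 8.1):** CGM, dosing, urine kits, surveys and, on Days 1-14, "Participants will take morning blood pressure readings, and keep dietary intake journal via Lifesum". The only meal mentioned is the first meal of the day, which sets the time of the dose.
- **Endpoints (10.3):** "The primary endpoint, average glucose, will be assessed by examining blood glucose (mg/dL) area under curve as measured by CGM", with the rule "Glucose data on days without canagliflozin treatment will serve as a control". The secondary endpoints are safety and tolerability, and urinary glucose.
- **Analysis:** analysis of variance, applied to CGM readings in the Synopsis and to blood tests in Section 13.
- **Size:** "10 individuals in each Arm", up to 20 in all.

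The Section 3 design figure, the materials list that the Synopsis refers to and Appendix A are not in the text available for this review.

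**The concern.** One of the two measures of the primary objective has no rule for obtaining it. To report on spikes, someone must decide which meals count as high-carbohydrate, how meal time is established, how long the post-meal window lasts and what makes an excursion a spike. The available text settles none of these. If they are settled with the CGM traces in view, a favourable spike result may reflect the definition chosen and not the drug. That would weaken any claim on the spike part of 7.1 and on hypothesis 2, in a trial with no placebo and at most 20 people.

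**Working it through.** **1. Tracing spikes through the plan.** The plan states no figure for this point, so the main check is textual.

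| Where | Spikes or a high-carbohydrate meal? |
|---|---|
| Title page, Study Design | Spikes named as a purpose |
| 6.4, hypothesis 2 | Spikes named |
| 7.1 | Spikes after a high-carbohydrate meal |
| Synopsis objective | No, average glucose only |
| Synopsis schedule and 8.1 | No such meal |
| 10.3 | No spike endpoint |
| Synopsis statistics and Section 13 | No spike analysis |

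That is three statements of intent against no scheduled meal, no endpoint and no analysis. The second measure in 7.1, glucose with and without drug, does have a counterpart: average glucose by CGM in 10.3.

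**2. What a later choice of definition could do.** The plan states no significance level, so all of the following is assumed:

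- one arm of n = 10, with no true effect;
- k = 8 candidate definitions (2 thresholds × 2 windows × 2 meal rules), with normal within-person changes and equal pairwise correlation ρ;
- a paired t-test at two-sided 5%, with critical value t(0.975, 9 df) = 2.262.

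A favourable result means a significant reduction, t < −2.262. With one definition its chance is 2.5%. With eight, the bounds are 2.5% (perfectly correlated) and 1 − 0.975^8 = 18.3% (independent). Simulating 200,000 null trials per setting gives 0.134 at ρ = 0.5, 0.103 at ρ = 0.7 and 0.0647 at ρ = 0.9, so about 13% to 6%. With four definitions it is about 8% to 5%.

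**3. Precision of a pre-specified endpoint.** The 95% CI half-width for a within-person change is 2.262 / √10 = 0.715, or about ±0.72 SD of the change per arm.

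**4. Which days are the control.** A within-person endpoint needs a control period. Arm B takes four doses every other day within Days 8-14, and the Synopsis places Day 15 at 24 hours after the last dose. Doses therefore fall on Days 8, 10, 12 and 14, and the days between are 9, 11 and 13. Take a daily-averaged CGM measure, let E be the dosing-day effect and let f be the fraction of it that remains on the days between. The documents do not give f, so the range 0 to 1 is shown. Assume CGM data end at Day 14, in line with the two-week enrolment in 10.2.

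- Literal 10.3 rule (4 dosing days against 7 + 3 = 10 other days): E − 3fE/10 = E(1 − 0.3f), which runs from 100% of E at f = 0 to 70% at f = 1.
- Period rule (Days 8-14 against Days 1-7): (4E + 3fE)/7 = E(4 + 3f)/7, which runs from 57% at f = 0 to 100% at f = 1.
- They are equal when 7 − 2.1f = 4 + 3f, so f = 3/5.1 = 0.59. Both are then 82% of E.

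In Arm A every day from 8 to 14 is a dosing day, so up to Day 14 the two rules agree.

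**The case against.** The strongest reply is that 7.1 may mean ordinary meals. The plan collects CGM data and a carbohydrate journal, lists CGM data as an efficacy criterion and ties hypothesis 2 to CGM. A free-living spike measure could be derived from these without any scheduled meal, and its definition can still be fixed in time. This stands: the data may suffice and what is missing is the rule. A reader might infer that the spike question can only ever be answered post hoc, but that follows only if nothing is fixed before the traces are seen.

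A meal may also be described in the figure, materials list or Appendix A, so its absence from the whole plan cannot be asserted. Even if one is described there, 10.3 and Section 13 would still hold no spike endpoint or analysis.

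Three further inferences are not supported:

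- **That both measures in 7.1 fail.** The word baseline is used loosely, since 8.1 applies it to the week before drug, but glucose with and without canagliflozin maps reasonably to the endpoint and control in 10.3.
- **That the chance of a misleading favourable result is about 27% to 13%.** Those figures count significant changes in both directions. Counting reductions only roughly halves them.
- **That the literal control rule simply dilutes the effect.** Relative to the period comparison, it gives the smaller contrast only if f exceeds about 0.59. Below that it gives the larger one. The rule can also be read as already meaning the baseline week, because 8.1 describes one and the Synopsis gives treatment as 7 days.

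**Conclusion.** The point holds for the spike part of the primary objective and for hypothesis 2, and should be fixed before data are seen. It is a mismatch between objective and endpoint in the available text. It does not mean that the primary objective as a whole cannot be answered, because average glucose has its endpoint in 10.3.

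The textual finding needs no numerical assumption. The illustrative size, about 13% to 6% against 2.5%, rests on the assumed eight definitions, their correlations, the 5% level and the paired t-test. The plan names analysis of variance and states no level. Confidence is medium, mainly because the figure, materials list and Appendix A could not be read.

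**What to change.** Before any CGM data are seen:

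1. Add to 10.3 one spike endpoint from the Lifesum journal and CGM: a stated carbohydrate cut-off for qualifying meals, a fixed post-meal window and one metric, for example peak rise or incremental area. State its rank relative to average glucose. Analyse it as within-person change from Days 1-7 to Days 8-14, by arm, with a 95% CI.
2. Reword 7.1 to refer to free-living high-carbohydrate meals.
3. If journal meal times are not reliable enough (8.1 asks for macronutrients and does not mention times), use percent of CGM time above one pre-fixed threshold, remove the meal wording from 7.1 and list spikes as secondary.
4. Align the Synopsis objective, hypothesis 2, 10.3 and Section 13. In Section 13, replace the reference to blood tests with CGM readings and name the spike analysis.
5. State in 10.3 that control means the Days 1-7 baseline week. Read literally, the present rule also takes in Arm B Days 9, 11 and 13, which may carry over drug effect and belong to the alternate-day regimen that hypothesis 3 tests. Say that the comparison estimates the effect of the regimen, and that this may be smaller or larger than the literal contrast depending on carryover.

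The cost is wording, one derived variable and IRB review of the amendment (14.1), with no new procedure or visit. Self-chosen meals are not standardised between weeks and journal timing is imprecise. Baseline always comes first, so time effects are not separated from drug. The result should be reported as an estimate. The fallback in step 3 avoids the timing problem but no longer speaks to meals.

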7.2 Secondary Objective

To assess the tolerability and side effects of the dosing protocol, and measure urinary glucose excretion.

8 Experimental plan

8.1 Study Design

This study is designed to mitigate the effects of glucose with intermittent oral Canagliflozin for healthy, non-diabetic volunteers of any sex who enroll in the study. The volunteers can be within 18-85 years of age at the time of enrollment. Participants will provide informed consent via AgelessRx EMR. If eligible, prescriptions will be provided online through the AgelessRx website (www.agelessrx.com). Participants will be randomized into two arms: Arm A will take 100 mg of canagliflozin each day for a total of 7 doses, while Arm B will take 150 mg of canagliflozin every other day for a total of 4 doses. Participants in Arm B will also be provided a pill cutter to use throughout the trial on the 300mg tablet.

All participants will begin the trial on the day that they apply a continuous glucose monitor (considered Day 0) and will be asked to take daily blood pressure reading. After one week of baseline readings, both arms will start their canagliflozin dosing protocols.

Participants will be asked to complete 7 total surveys to outline side effects and tolerability, one each day starting after their canagliflozin consumption.

Participants will be asked to complete a dietary intake journal through Day 0 – Day 14. Lifesum (<https://lifesum.com/>) should be used to track Carbohydrate/Protein/Fat consumption. Participants will share their dietary intake journal twice over their participation (Day 7 & Day 14).

8.2 Cost of Participation

This trial will be sponsored under the organization AgelessRx. There will be no cost to the participant to participate.

8.3 Number of Centers and Subjects

We will recruit up to 20 healthy participants to participate in the study. Online prescriptions will be provided by [name] via the AgelessRx website (www.agelessrx.com). Our partner pharmacy with the ability to ship to most states nationwide will provide the prescriptions and CGMs to participants. Efficacy testing will be performed by AgelessRx. To measure glucose, the Abbott Laboratories Freestyle Libre CGM (<https://www.freestyleprovider.abbott/us-en/freestyle-libre-2.html>) will be used. For urinalysis, Access Medical Labs Glucose, Urine (<https://www.rupahealth.com/lab-tests/access-medical-labs-glucose-random-urine#description>) will be used.

8.4 Estimated Study Duration

We anticipate the study will last a maximum of 90 days.

9 Subject Selection

9.1 Number of Subjects

Up to 20 individuals

9.2 Inclusion Criteria

1. Age 18-85
2. Any sex
3. Any ethnicity
4. Interest in taking Canagliflozin
5. Approved by the AgelessRx Medical team to take Canagliflozin
6. Willing and technically able to use and operate a CGM
7. Own a CGM-compatible phone

8. Relatively good health with only well-managed chronic diseases (hypertension, coronary artery disease, type II diabetes, etc.) clinically stable
9. Adequate cognitive function to be able to give informed consent

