11.2 Control Drug

No placebo will be used in this trial.

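### Participants run the outcome CGM on their own phones with no masking or keep-your-habits instruction in the supplied text, so a behaviour change between the baseline and drug weeks is confounded with drug effect

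*Combined protocol and SAP*

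**What the plan says.** The participant operates the outcome device. The inclusion criteria (9.2) ask for people who are "Willing and technically able to use and operate a CGM" and who "Own a CGM-compatible phone"; the Synopsis repeats the second requirement ("They also require a CGM-compatible mobile device"). Section 8.3 names the device ("To measure glucose, the Abbott Laboratories Freestyle Libre CGM") and mentions no masked mode.

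The only instruction on the sensor in the supplied text is in the Synopsis, Methodology, for Day 0: "Participants will attach a continuous glucose monitor (CGM) and follow instructions for calibration period". Nothing there or in 8.1 covers viewing the readings, acting on them, or keeping diet and activity constant. Section 8.1 has diet recorded in Lifesum from Day 0 to Day 14 and shared on Days 7 and 14.

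The order of periods is the same for everyone (8.1): "After one week of baseline readings, both arms will start their canagliflozin dosing protocols". Section 10.3 makes CGM area under the curve the primary endpoint and takes days off canagliflozin as the control. Section 11.2 adds: "No placebo will be used in this trial". The analysis is an analysis of variance with no model terms named (Synopsis; section 13).

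**The concern.** If the phone shows the readings, the display feeds back to participants the very quantity that the trial tests. By Day 8 each of them has had a week in which to see which meals raise their glucose, while also logging macronutrients. The protocol itself says that behaviour can act on glucose spikes (6.3): "In healthy, non-diabetic individuals, the main way to mitigate blood sugar spikes is to rely on diet and exercise".

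Time on the sensor and treatment are aligned in both arms: the first week is untreated and the second is treated. With no untreated group running alongside, the before-after contrast cannot separate a drug effect from a change in eating or activity that happens to fall between the weeks. Randomising between two active regimens does not help, because both arms share the same sensor exposure and order. The hypotheses in 6.4 that the drug lowers CGM glucose, and that alternate-day use works, both rest on the contrast with untreated days. At stake is whether a fall in average glucose can be credited to canagliflozin.

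**Working it through.** The plan gives no sample-size calculation, alpha, effect size or SD, so there is no figure of its own to reproduce. The first part below is reasoning from the text; the rest is illustration.

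**1. What enters the contrast.** Write the drug-week mean minus the baseline-week mean as D = drug effect + (behaviour effect in Days 8-14 − behaviour effect in Days 1-7). Only the difference between the weeks biases D. A reaction that starts with the sensor on Day 0 and stays constant cancels. For the difference between arms, the bracket drops out if it is equal in A and B.

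**2. How often a pure behaviour shift would be declared a drug effect.** From the documents: n = 20 in total, 10 per arm (Synopsis). Assumed: true drug effect 0; a two-sided paired t-test at 5%; SD of the within-person change in weekly mean of 4 to 8 mg/dL; a fall s of 0.5 to 3 mg/dL. The noncentrality is s / (SD/√n), and the rejection probability comes from the noncentral t distribution with n − 1 degrees of freedom (critical value 2.093 for n = 20, 2.262 for n = 10). Example: n = 20, s = 2, SD = 4 gives 2 / (4/√20) = 2.236 and a rejection probability of 0.56.

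| n | fall (mg/dL) | SD 4 | SD 6 | SD 8 |
|---|---|---|---|---|
| 20 | 0.5 | 8% | 6% | 6% |
| 20 | 1 | 19% | 11% | 8% |
| 20 | 2 | 56% | 29% | 19% |
| 20 | 3 | 89% | 56% | 36% |
| 10 | 1 | 11% | 8% | 6% |
| 10 | 2 | 29% | 16% | 11% |
| 10 | 3 | 56% | 29% | 19% |

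With no shift the figure is 5% (2.5% in the direction of a fall).

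**3. Whether the baseline week alone could reveal learning.** Fit a slope to daily mean glucose over Days 1-7, where the squared day deviations sum to 28. With an assumed day-to-day SD of 6 mg/dL, independent days and 20 people, SE = √(36 / (20 × 28)) = 0.25 mg/dL per day. If learning is linear, a shift of 2 or 3 mg/dL between week midpoints, which lie 7 days apart, is a slope of 2/7 = 0.29 or 3/7 = 0.43 mg/dL per day. Dividing by the SE (0.2535 unrounded) gives 1.13 or 1.69, so two-sided 5% power is about 20% or 39% (normal approximation). Correlated days or person-to-person variation in slope would generally lower it.

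**The case against.** The strongest reply is that the direction of any bias is not established. Watchfulness may be highest in the first days and then fade, or people on an open-label drug may eat more freely; either would work against canagliflozin. A reader might infer that the sensor must lower glucose in the second week. The documents do not show this: the sentence in 6.3 is about diet and exercise, not about the effect of seeing readings. This part of the objection stands.

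A reader might also take the control to be only the earlier, untreated week. Section 10.3 says days without canagliflozin and does not say earlier. Arm B takes 4 doses over the 7 days from Day 8 to Day 14, leaving 3 undosed days inside the drug week. These share the later calendar time, but they exist in one arm, are open to carry-over, and are not stated to be control days or otherwise.

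Nor is it right that a behaviour effect would be wholly indistinguishable from drug effect. The Lifesum log could show a large change in intake, and urine glucose before and after dosing gives supporting evidence that the drug acted. Both are partial. No analysis of the log is stated, it does not record activity under 8.1, and urinary glucose does not say how much of a fall in average glucose came from the drug.

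Finally, an instruction may exist elsewhere. Section 10.1 has the coordinator give further instruction, and the Synopsis mentions calibration instructions; neither these nor the consent appendix were supplied. What the phone displays is also not described. The absence can be asserted only for the text at hand.

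**Conclusion.** The point holds as a risk of confounding. In the supplied text nothing masks the readings or fixes behaviour, the order of periods is fixed, and there is no concurrent untreated control, so any change in behaviour between the weeks passes into the primary contrast. Its sign and size are unknown. The percentages rest on an assumed SD, an assumed shift and an assumed paired test. They range from close to the nominal 5% for a shift of 0.5 mg/dL to 89% for 3 mg/dL with the smallest SD, and none of them is a forecast. The A-versus-B comparison is largely protected if the shift is equal in both arms. The change is worth making before enrolment because masking cannot be added afterwards.

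**What to change.** In 8.1, instruct participants to keep their usual eating and activity from Day 0 to Day 14 and not to adjust them to sensor readings or Lifesum totals, apart from any high-carbohydrate meal that the protocol specifies under 7.1. Hide the running readings from the participant where the app allows, leaving safety alerts as they are. If the unsupplied participant materials already say this, bring the wording into 8.1.

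In section 13, compare logged carbohydrate and energy intake between Days 1-7 and Days 8-14. Report this and the Day 1-7 glucose slope as descriptive context beside the primary result. State that a flat slope does not exclude learning, given its power of about 20-39% under the assumptions above.

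The cost is one instruction, an app setting where available and a short descriptive table; no change to dose, visits or sample size is needed. The limits should be stated too: the instruction cannot be enforced, masking depends on the app, and the checks can only detect a shift, not correct for it or separate the effect of the display from that of diet logging.
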